**Randomized Double Blinded Study Comparing Timing of PEC Block  
for Post-Operative Pain in Bilateral Mastectomy Patients**

NCT Number: 03653988

[name]

Document Date: October 3, 2018

The current standard of care at the [REDACTED] is to receive a pectoralis nerve block PEC I/II block prior to surgery for mastectomy and reconstruction cases. We will compare whether patients will have better pain control if they were to receive (PEC I/II block) before surgery or after the mastectomy. Patients undergoing mastectomies at the [REDACTED] receive general anesthesia and a regional block for pain control. The most commonly employed regional anesthetic technique is a PECS I/II block to anesthetize the pectoral, intercostobrachial, third to sixth intercostal and long thoracic nerves. The PECS I/II blocks are pectoralis field blocks where local anesthetic medication is injected under ultrasound guidance between the tissue planes of pectoralis major and minor muscles (PECS I) and in the plane of the serratus anterior muscle at the level of the third rib (PECS II). We will randomize patients into two groups and blind the patient and the research assistant collecting the data. Group I will have the block performed after induction of general anesthesia and prior to surgical incision by the anesthesiologist. Group II will have the block administered by the surgeon after mastectomy is performed and before reconstruction. On the day of surgery, we will have patients fill out forms to measure pain catastrophizing and depression and anxiety. We would like to measure if there is any difference in postoperative pain scores (visual analogue scale)-immediately post-surgery in post-anesthesia care unit(PACU), and then on the admission unit every 4 hours for the first twenty four hours or on discharge (whichever time-point occurs sooner) and we will collect the average pain scale of the day on post-op day (POD) 2,3,5 and 7 via patient communication electronic message in RedCap. We will also measure intraoperative and post-operative narcotic use (converted to morphine equivalents), post-operative nausea and vomiting, length of (PACU) stay. In addition, we will collect pain scores and pain catastrophic scale on POD 14 after surgery at their clinic visits to the surgeon. Other data collected will include time taken to perform block, post-operative infection rate and post-operative flap necrosis rate.

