**Randomized Double Blinded Study Comparing Timing of PEC Block
for Post-Operative Pain in Bilateral Mastectomy Patients**

NCT Number: 03653988

[name]

Document Date: October 3, 2018

Statistical Plan

The primary objective is to evaluate whether administration of a PEC I/II block post-mastectomy reduces average pain scores during post anesthesia care unit (PACU) and inpatient stay when compared to administration pre-mastectomy. Accordingly, a sample size of 34 patients ensured 80% power to detect a mean difference in pain scores of at least 2 as being clinically significant. Calculations were based on 1:1 randomization, a common standard deviation of 2, and using a two-sided, two-sample t-test evaluated at a 5% significance level. The secondary outcomes were average pain scores on POD 2, 3, 7, 14, 60 and 180 days, postoperative narcotic requirements, PACU and inpatient length of stay, complications, and readmission rates.

Chi-squared or Fisher's exact tests (where appropriate) were used to compare categorical variables, and Wilcoxon rank sum tests were used to compare continuous variables between treatment groups. Linear mixed effects regression models were used to assess treatment group differences in terms of pain scores, number of pills taken post-operatively, and PCS scores. Random effects were included to account for the longitudinally correlated nature of repeat assessments within a patient over time. All tests were two-sided and assessed for significance at the 5% level using SAS v9.4 (SAS Institute, Cary, NC).

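### Optional improvement, not an error: day-of-surgery pain catastrophizing is collected, but no baseline covariate is named in the SAP's models for pain and PCS

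*SAP*

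**What the plan says.** The protocol describes two measurements of pain catastrophizing. The first is at baseline: "On the day of surgery, we will have patients fill out forms to measure pain catastrophizing and depression and anxiety". The second is at follow-up: "we will collect pain scores and pain catastrophic scale on POD 14 after surgery at their clinic visits to the surgeon". It describes no pre-operative pain score, so the day-of-surgery forms are the only baseline scores in the documents.

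The protocol also fixes when treatment starts in each arm: "Group I will have the block performed after induction of general anesthesia and prior to surgical incision by the anesthesiologist", and "Group II will have the block administered by the surgeon after mastectomy is performed and before reconstruction".

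In the second paragraph of the SAP's Statistical Plan, mixed models are to assess "treatment group differences in terms of pain scores, number of pills taken post-operatively, and PCS scores". The terms named are treatment group and random effects for repeated measurements. The text does not say whether the day-of-surgery score is a covariate, a first repeated response, or unused. It does not expand PCS; reading it as the pain catastrophizing scale is an inference from the protocol.

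The first paragraph sizes the trial at 34 patients for a pain difference of 2: "Calculations were based on 1:1 randomization, a common standard deviation of 2". PCS is not among the secondary outcomes, which are the later pain scores and "postoperative narcotic requirements, PACU and inpatient length of stay, complications, and readmission rates".

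**The concern.** A prognostic score measured before treatment can be used to sharpen a randomised comparison at no cost in patients. In both arms the block comes after induction or later, so a form completed before induction is pre-treatment for everyone. Two uses are left unspecified.

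(a) **PCS at POD 14.** The documents give PCS only two times, one of them on the day of surgery. If both enter as responses and the group main effect is tested, a score that treatment cannot have affected is averaged into the estimate. The SAP does not say it will do this, but it does not rule it out.

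(b) **Primary pain comparison.** If day-of-surgery PCS is related to early pain, adjusting for it narrows the confidence interval. With 17 patients per arm the unadjusted 95% interval is about ±1.40 points around a target difference of 2, so extra precision would be useful.

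Part (a) concerns an outcome that is not on the secondary list and cannot alter the primary conclusion. Part (b) bears on the precision of the primary result, not its validity.

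**Working it through.** **Inputs from the SAP:** difference 2, common SD 2, 34 patients 1:1 (17 per arm), two-sided 5% t-test. **Assumed:** r, the correlation of day-of-surgery PCS with average PACU and inpatient pain; ρ, the correlation of day-of-surgery with POD 14 PCS; and a 1-SD effect on POD 14 PCS. The documents give none of these.

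**1. The SAP's own figure.** Standardised difference d = 2/2 = 1; noncentrality d × √(n/2) = √(17/2) = 2.915; 32 df. Noncentral-t power is 80.7% with 17 per arm and 78.1% with 16, so 34 is reproduced. The 95% half-width is t(0.975, 32) × 2 × √(2/17) = 2.037 × 0.686 = 1.40.

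**2. Adjusted primary comparison, no forms missing.** The residual SD is 2√(1 − r²), so d becomes 1/√(1 − r²), with 2n − 3 = 31 df. Chance imbalance in the covariate multiplies the variance of the group difference by 1 + t²/(2n − 2), where t follows a t distribution on 2n − 2 df. Power and half-width are averaged over t.

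| r | Power | 95% half-width |
|---|---|---|
| unadjusted | 80.7% | 1.40 |
| 0 | 79.4% | 1.42 |
| 0.2 | 81.0% | 1.39 |
| 0.3 | 83.0% | 1.36 |
| 0.5 | 89.4% | 1.23 |

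Adjustment breaks even at r of about 0.18. Leaving out the imbalance term gives higher figures (80.6/82.2/84.1/90.3%); the table is the more cautious version.

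**3. Missing baseline forms.** A complete-case adjusted model loses every patient without a form. Overall-mean filling replaces a missing score with the mean of all observed scores, ignoring arm. The filling results come from 400,000 simulated trials per setting, with forms missing at random.

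| Handling | r = 0 | 0.2 | 0.3 | 0.5 | Break-even r |
|---|---|---|---|---|---|
| Complete case, 1 lost per arm | 76.6% | 78.3% | 80.4% | 87.3% | 0.31 |
| Complete case, 2 lost per arm | 73.6% | 75.4% | 77.5% | 84.9% | 0.40 |
| Mean filled, 1 missing per arm | 79.3% | 80.9% | 82.8% | 88.8% | – |
| Mean filled, 2 missing per arm | 79.3% | 80.8% | 82.4% | 88.1% | – |

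With mean filling, simulated type I error was 4.97% to 5.03% and the average estimate was 1.00 times the true effect.

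**4. PCS at POD 14 (1-SD effect, 17 per arm).** Averaging both times, the expected group difference is (0 + 1)/2 = 0.5, and the SD of the two-time mean is √((1 + ρ)/2). The change score has SD √(2 − 2ρ). ANCOVA is computed as in step 2.

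| Contrast | Effect estimated | ρ = 0.3 | 0.5 | 0.7 |
|---|---|---|---|---|
| Main effect over both times | half | 42% | 37% | 34% |
| POD 14 alone | whole | 81% | 81% | 81% |
| Change from day of surgery | whole | 67% | 81% | 95% |
| ANCOVA on day-of-surgery score | whole | 83% | 89% | 97% |

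**The case against.** The strongest reply is that nothing in the SAP is wrong. Leaving out covariates in a 34-patient trial is a legitimate choice, and the sample size is correct for the test it was based on. That stands, and it is why this is offered only as an improvement.

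On (a), the SAP does not say it will test a main effect over both times, and its reference to repeated assessments may mean that the day-of-surgery score is already a response. The ordinary group-by-time contrast, change from day of surgery, would estimate the whole effect with 67/81/95% power. So the 42/37/34% figures describe the worst reading, not the likely one. Even so, ANCOVA has more power than the change score at each ρ shown, and the SAP still needs to name its contrast. The 1-SD effect is only illustrative.

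On (b), the benefit rests on an unknown r. At r = 0.2 the gain is 81.0 − 80.7 = 0.3 points of power; at r = 0 there is a loss. The documents give no reason to prefer PCS to the depression and anxiety forms collected the same day. The protocol says the forms are completed on the day of surgery, not expressly before induction. The SAP is also written in the past tense, so the analysis may already have been done, in which case adjustment would be post hoc. These points limit the expected benefit and set conditions on the change; none makes the adjusted analysis invalid.

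**Conclusion.** The point holds as a low-cost option. Data already collected could give a more precise primary comparison and a properly defined PCS comparison, and the SAP specifies neither.

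For primary pain the benefit is conditional: a loss of about 1.3 points of power at r = 0, a gain of 2.3 points at r = 0.3 (83.0 − 80.7) and of 8.7 points at r = 0.5 (89.4 − 80.7), provided no patient is dropped for a missing form. These figures treat the outcome as one averaged pain score per patient, as the sample size calculation does.

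For PCS, the case for naming the contrast does not depend on any correlation: a main effect over both times would halve the estimate. This part rests on PCS meaning the pain catastrophizing scale and on the day-of-surgery form being pre-treatment.

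**What to change.** Add two or three sentences to the second paragraph of the Statistical Plan:

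- Expand PCS. Estimate its group difference at POD 14 by ANCOVA on the day-of-surgery score, or by a mixed model with equal baseline means in the two arms, and not by a main effect that averages in the day-of-surgery score.
- Include day-of-surgery PCS as the single baseline covariate in the primary pain model, once it is confirmed that the form was completed before induction. The contrast is the group difference in average PACU and inpatient pain.
- Fill missing baseline forms with the overall mean, ignoring arm, so that every patient stays in the analysis.
- Report the unadjusted estimate as a sensitivity analysis. If outcome data have already been examined, label the adjusted analysis post hoc.

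The cost is one degree of freedom and no new data. If PCS proves unrelated to pain, about 1.3 points of power are lost (80.7% to 79.4%). A complete-case model with one form missing per arm would instead lose about 4 points (80.7% to 76.6%), which is why the missing-form rule belongs in the same change.

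### The SAP's only repeated-measures medication analysis is of a raw pill count with no stated source, although the protocol measures narcotic use in morphine equivalents

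*SAP*

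**What the plan says.** The Statistical Plan in the SAP uses linear mixed models to assess "treatment group differences in terms of pain scores, number of pills taken post-operatively, and PCS scores". It explains the model in these words: "Random effects were included to account for the longitudinally correlated nature of repeat assessments within a patient over time". It does not say which drugs the pills are, at what strength, over which days, or who records them.

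Medication appears in one other place in the SAP. After the pain scores, the secondary outcomes continue with "postoperative narcotic requirements, PACU and inpatient length of stay, complications, and readmission rates". No unit, window or named method is attached to the narcotic item. As a continuous variable it would come under the general rule that "Wilcoxon rank sum tests were used to compare continuous variables between treatment groups".

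The protocol defines its medication measure as "intraoperative and post-operative narcotic use (converted to morphine equivalents". It gives no collection times for that measure and does not mention pills. Its electronic messages are described as collecting the "average pain scale of the day on post-op day (POD) 2,3,5 and 7".

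**The concern.** The two documents describe medication use in different units, and the cruder unit is the one that receives the longitudinal analysis. A pill count gives equal weight to pills of different drug or strength. As worded, it does not say that the pills are narcotics, and it leaves out any narcotic given by another route. Two patients who each take 10 pills, one at twice the strength of the other, have the same outcome in the model and a two-fold difference in dose.

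At stake is the reading of a secondary comparison. If the counts are reported as evidence about narcotic use, the model could show a difference where doses are equal, or none where doses differ. Because drugs, days and source are undefined, they could also be settled after the data have been seen.

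**Working it through.** **Plan's own figure.** The only computed figure is the sample size of 34. With a difference of 2, SD 2, two-sided 5% and 1:1 allocation, the two-sample t-test has power 0.807 at 17 per arm and 0.781 at 16 per arm, so 34 in total reproduces. It concerns the primary pain outcome and has no bearing on the pill count.

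**The documents side by side.**

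| Item | Protocol | SAP |
|---|---|---|
| Narcotic use | Measured, in morphine equivalents; no days given | Listed secondary outcome; no unit; Wilcoxon by default |
| Pill count | Not mentioned | In the mixed model; not in the secondary list |
| PACU, then 4-hourly to 24 hours or discharge | Pain scores | – |
| POD 2, 3, 5, 7 messages | Average pain | Pain on POD 2, 3 and 7 listed; POD 5 not |
| POD 14 visit | Pain scores and catastrophizing scale | Pain on POD 14 listed |

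No dated collection point in the protocol names a pill count, and the term morphine equivalents does not occur in the SAP.

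**What a count can hide.** Suppose pills come in two strengths, the stronger with r times the opioid content of the weaker, and let q be the stronger pill's share of an arm's pills. Mean dose per pill, in units of the weaker pill, is 1 + q(r − 1). With equal counts in the two arms, the dose ratio is

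[1 + q₂(r − 1)] / [1 + q₁(r − 1)].

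The documents give neither r nor q, so every value below is an assumption.

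| q₁ | q₂ | r | Dose ratio at equal counts |
|---|---|---|---|
| 0.50 | 0.50 | any | 1.00 |
| 0.25 | 0.75 | 1 | 1.00 |
| 0.25 | 0.75 | 1.5 | 1.375/1.125 = 1.22 |
| 0.30 | 0.50 | 2 | 1.5/1.3 = 1.15 |
| 0.25 | 0.75 | 2 | 1.75/1.25 = 1.40 |
| 0.25 | 0.75 | 3 | 2.5/1.5 = 1.67 |

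In every row the expected difference in pill count is zero. The converse also holds. If doses were equal with q₁ = 0.30, q₂ = 0.50 and r = 2, the second arm would take 1.3/1.5 = 0.87 times as many pills, an apparent saving of 13% with no saving in dose.

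**The case against.** The strongest reply is that nothing has been displaced. The protocol measures narcotic dose, the SAP lists narcotic requirements as a secondary outcome, and the Wilcoxon rule supplies a test. On that reading the pill count is an additional variable. This stands: a reader might infer that the SAP has dropped narcotic dose, and the documents do not support that. The listed outcome still has no stated unit, however, and it does nothing for the mixed model.

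A reader might also infer that there are no repeated counts to model, or that the messages ask about pain and nothing else. The documents do not show this either. The protocol is one paragraph, it gives no collection days for any narcotic use, and the SAP already plans pain assessments at 60 and 180 days that the protocol does not mention. Silence on pills is not evidence that counts were not collected; they may even be the raw input to the conversion. What remains is that the source is unstated.

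Third, allocation is randomized, and no mechanism is offered for a systematic difference in strength between arms. That is fair. With about 17 patients per arm a chance imbalance is plausible, but its size is unknown.

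Finally, the stated primary objective is pain in PACU and during the inpatient stay, and less opioid use after discharge is not a stated objective. That limits the importance of the point to a secondary analysis.

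**Conclusion.** The point holds as a low-cost improvement to a secondary analysis. The medication variable that receives the repeated-measures model has no stated drug, strength, days or source, is absent from the SAP's own secondary list, and is not in the unit that the protocol specifies.

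The size cannot be estimated from the documents. The range of 1.00 to 1.67 rests wholly on assumed strengths and shares, and it includes no effect at all: with a single drug and strength, or the same mix in both arms, nothing is lost. No single figure, such as the 15% scenario, should be read as a bias in this trial. The primary comparison and the sample size are untouched.

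**What to change.** In the SAP, make narcotic use in morphine equivalents the analysed medication outcome in both places: as the stated unit of the listed narcotic outcome, with its time window, and as the response in the mixed model in place of the raw count. Keep the pill count as a descriptive summary.

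Name the source and the days, and record drug and strength with each count. For patients still in follow-up, the existing POD 2, 3, 5 and 7 messages are one possible place. The SAP's pain outcomes omit POD 5, so the days should be stated explicitly. The SAP is written in the past tense; where follow-up is already complete, conversion is possible only if drug and strength were recorded, and otherwise the count should be reported as descriptive.

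Daily dose may be skewed, so keep the Wilcoxon comparison of total morphine equivalents alongside the linear mixed model.

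The cost is SAP wording, slightly more patient burden, and a conversion step that the protocol already plans.
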